1. INTRODUCTION

Central venous catheters (CVCs) are indispensable in modern critical care as they are highly reliable as intravenous access for administration of vasopressors, inotropes, irritant solutions, total parenteral nutrition and for haemodynamic monitoring. The average central line utilisation ratios in the ICUs across 45 countries were reported at 0.525 (Rosenthal et al., 2021). CVC usage is associated with complications, including central line-associated bloodstream infections (CLABSIs).

The rate of CLABSI is reported at 4.45 per 1000 central line days in ICUs across 45 countries from 2013 – 2018 (Rosenthal et al., 2021). This in turn, is translated to increased healthcare costs and mortality. One of the strategies to reduce the incidence of CLABSI is the use of antimicrobial-impregnated CVCs. These antimicrobial-impregnated CVCs, which can be coated with either antibiotics (e.g. rifampin, minocycline, etc.) or antiseptics (e.g. chlorohexidine, silver sulphadiazine, benzalkonium chloride, etc.) or both, are proposed to be able to reduce the incidence of CLABSI by inhibiting microorganism colonisation on CVCs. A meta-analysis published in 2018 concluded that antimicrobial-impregnated CVCs were significantly effective in reducing CLABSIs and catheter colonisations (Wang et al., 2018). Nevertheless, its efficacy and beneficial effects, particularly in terms of patients' outcome had not been homogeneously demonstrated across literature. Moreover, antimicrobial-impregnated CVCs are more expensive compared to non-impregnated ones, and hence its cost-effectiveness remains doubtful.

To date, in our local setting, no study evaluates the efficacy and economic impact of antimicrobial-impregnated CVCs and on patients' outcome. Cost-effectiveness evaluation is important to provide value-based care in clinical practice. This study aims to evaluate the clinical and economic treatment of antimicrobial-impregnated CVCs vs Non-impregnated CVCs in prevention of CLABSI.

1.1 Research Questions

1. Is there any difference in central line-associated bloodstream infection (CLABSI) rates between patients using antimicrobial-impregnated central venous catheters (CVCs) and non-impregnated CVCs in Malaysia adult Intensive Care Unit (ICU)?

2. Does the use of antimicrobial-impregnated central venous catheters (CVCs) in central line-associated bloodstream infection (CLABSI) prevention in Malaysia adult Intensive Care Unit (ICU) affect patient length of stay when compared to non-impregnated CVCs?
3. Does the use of antimicrobial-impregnated central venous catheters (CVCs) in central line-associated bloodstream infection (CLABSI) prevention in the adult Intensive Care Unit (ICU) setting affect healthcare costs when compared to non-impregnated CVCs?
4. How antimicrobial resistance features of the bacteria causing central line-associated bloodstream infection (CLABSI) may differ in patients using antimicrobial-impregnated central venous catheters (CVCs) compared to non-impregnated CVCs?

2. OBJECTIVES

Primary objective:

- To compare the incidence of central line-associated bloodstream infection (CLABSI) rate in patients using antimicrobial-impregnated central venous catheter (CVCs) and non-impregnated CVCs in Malaysia adult Intensive Care Unit (ICU)

Secondary objectives:

- To determine the length of stay of patients using antimicrobial-impregnated central venous catheter (CVCs) vs non-impregnated CVCs in Malaysia adult Intensive Care Unit (ICU)
- To undertake a cost-effectiveness analysis in prevention of central line-associated bloodstream infection (CLABSI) between patients using antimicrobial-impregnated central venous catheters (CVCs) and non-impregnated CVCs in Malaysia adult Intensive Care Unit (ICU)
- To compare the antimicrobial resistance features of the bacterial species that caused central line-associated bloodstream infection (CLABSI) between patients using antimicrobial-impregnated central venous catheter (CVCs) and that of non-impregnated CVCs in Malaysia adult Intensive Care Unit (ICU)

3. METHODOLOGY

3.1 Study Location

The study will be conducted in the adult Intensive Care Unit (ICU) of Universiti Malaya Medical Centre (UMMC), which is a mixed medical/surgical ICU.

3.2 Study Period

The study will be conducted over a period of one year.

3.3 Study Design

The study will be conducted as a randomised-controlled trial.

3.4 Study Population

Inclusion criteria:

- Patients aged 18 years old and above who are admitted to the ICU of UMMC during the study period
- Patients who require a CVC during ICU stay

Exclusion Criteria:

- Patients who refuse to participate in the study
- Patients with known hypersensitivity reaction to CVC materials
- Patients with pre-existing diagnosis of central line-associated bloodstream infection (CLABSI) upon admission to the ICU
- Patients with pre-existing bloodstream infection upon admission to the ICU
- Patients with a pre-existing CVC, where sterility during placement may be compromised (e.g. in an emergency situation)
- Patients with indwelling CVC less than 48 hours
- Patients who had poor compliance to catheter bundle care during CVC handling throughout the indwelling catheter period
- Patients who require > 1 CVC or other central venous access

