3.5 Sampling Method

All adult patients who require a CVC insertion as part of their standard routine treatment in ICU will be recruited. After the recruitment, the patients will be randomly assigned to one of the two different groups using a computer: control group who receives non-impregnated CVC and investigational group who receives antimicrobial-impregnated CVC.

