3.6 Sample Size

Our local data at ICU, UMMC reported the incidence of CLABSI per 1000 catheter days in the first 6 months of 2022, to be 12.18. Using SAS® for sample size calculation, in order to detect a clinically significant reduction of CLABSI by 30%, and assuming a two-sided type I error protection of 0.05 and a power of 0.80, we calculated a sample size of 50 patients is required. To incorporate a 10% drop out rate, we therefore aim to recruit 55 patients in each arm (antimicrobial-impregnated CVCs, n=55; non-impregnated CVCs, n=55). This will make up to a total sample size of 110.

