3.7 Variables/ Parameters

3.7.1 Dependent Variables

3.7.1.1 Primary Outcome

The primary outcome investigated is the central line-associated bloodstream infection (CLABSI) rate, expressed in cases per 1000 catheter days. The diagnosis of CLABSI will be based on the CDC-NHSN definition.

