3.7.2 Other Parameters

Baseline patient data will be included as concomitant study parameters. Relevant patient and clinical data including basic demographic information (age, gender, and ethnicity), known underlying diseases, previous antibiotic exposure within 90 days, and admission date will be extracted from the clinical database for correlation and risk factor analyses.

For patients diagnosed with CLABSI, information including the number of days a patient spent in the hospital prior to strain isolation, number of days and type(s) of antibiotics used in said patient, hospital-generated antibiograms for each strain, patient risk factors for nosocomial infection associated with an isolate, previous surgeries or hospitalizations of the patient prior to isolation, location of a patient within the hospital prior to strain isolation and ICU admission, and any other information pertinent to a specific strain that will not identify a patient will be collected.

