3.9 Data Analysis

The data will be analysed using the SPSS Software. Descriptive statistics will be expressed as percentages unless otherwise stated. Categorical variables will be expressed as percentages and compared using the Chi-square or Fisher's exact test, whichever is appropriate. Variables with a univariate test value of less than 0.05 (p-value) will be included in a multivariate analysis using a logistic regression model. Odds ratios (OR) and 95% confidence intervals (CI) will be calculated to identify the risk factors associated with the development of CLABSI in patients. In all instances, a p-value of less than or equal to 0.05 will be considered significant.

FUNDING

This study will be funded by Teleflex Research Grant (RM50000).

RESEARCH DATA MANAGEMENT

All data collected will be handled confidentially according to the Good Clinical Practice Guidelines. The paper case report forms will be stored within a locked cabinet at the Department of Anaesthesiology, Faculty of Medicine, Universiti Malaya. The electronic case report forms will be kept in a password-protected laptop. Only the study investigators will have access to the research data. The data will be kept for seven years upon completion of study. The results of the study will be reported in a thesis. The results will also be presented in conferences and published in scientific journals.

POTENTIAL RESEARCH IMPACT

The usage of antimicrobial-impregnated central venous catheters (CVCs) among adult critically ill patient in the Intensive Care Unit (ICU) can reduce central line-associated bloodstream infections (CLABSIs) and this will translate to reduced patients' length of stay and healthcare costs.

GANTT CHART

	2023												2024											
Research Activities	3	4	5	6	7	8	9	10	11	12	1	2	3	4	5	6	7	8	9	10	11	12		
Ethics submission	█	█																						
Patient recruitment			█	█	█	█	█	█	█	█	█	█	█	█										
Data collection			█	█	█	█	█	█	█	█	█	█	█	█										
Data analysis															█	█	█							
Completion and submission of manuscript																		█	█	█				
Publication and scientific presentations																					█	█		

REFERENCES

- Alotaibi, N. H., Barri, A., & Elahi, M. A. (2020). Length of Stay in Patients With Central Line-Associated Bloodstream Infection at a Tertiary Hospital in the Kingdom of Saudi Arabia. *Cureus, 12*(10). <https://doi.org/10.7759/CUREUS.10820>

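### Section 3.4 excludes patients on bundle compliance and catheter dwell, which are known only after randomisation, and no analysis population is named to keep them in

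*Combined protocol and SAP*

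**What the plan says.** All references are to the combined protocol and SAP.

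- **Order of events (3.5).** Patients who need a catheter inserted are recruited, and "After the recruitment, the patients will be randomly assigned to one of the two different groups using a computer". The arm determines which catheter is then placed, so randomisation comes before any dwell or handling of the study catheter.
- **Exclusions (3.4).** The list includes "Patients who had poor compliance to catheter bundle care during CVC handling throughout the indwelling catheter period", "Patients with indwelling CVC less than 48 hours" and "Patients who require > 1 CVC or other central venous access".
- **Primary outcome (3.7.1.1).** The CLABSI rate is "expressed in cases per 1000 catheter days".
- **Variables collected (3.7.2).** The patient-level list runs through demographics, "known underlying diseases, previous antibiotic exposure within 90 days, and admission date will be extracted from the clinical database". Neither bundle compliance nor additional lines is named.
- **Analysis (3.9).** Tests and a logistic model are described. No analysis population is defined, and nothing is said about a randomised patient who later meets an exclusion.
- **Drop-out (3.6).** A 10% allowance raises 50 per arm to 55. Drop-out is not defined or linked to these exclusions.

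No section gives a threshold for poor compliance, says who judges it or when, or describes masking.

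**The concern.** Randomisation protects the comparison only if the patients compared are those who were randomised. An exclusion that depends on what happens after allocation replaces that comparison with one between two selected subsets.

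The compliance criterion is the main route. It is discretionary, and it covers the same days in which the outcome occurs. Lapses in bundle care plausibly relate to CLABSI risk, and a positive culture may itself prompt a search for lapses. Without masking, the judgement could be made with both arm and outcome known. Few CLABSIs are expected per arm, so a handful of such decisions can move the primary estimate materially.

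The other two bullets carry less weight. The dwell rule is also settled only after randomisation but has little scope to remove CLABSI cases. The bullet on more than one line has no time limit: it can be screened at entry for an existing need, but could also be applied later, and whether a replacement line counts is not stated.

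**Working it through.** **Can each criterion be known at randomisation?**

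- Bundle compliance over the whole catheter period: no, on any reading.
- Dwell under 48 hours: no, if it refers to the study catheter. The bullet does not say so, but that is the natural reading, because pre-existing catheters have their own bullet and recruits still need an insertion.
- More than one line: yes for a need already present, no for one that arises later.

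**How far could removals move the estimate?** The plan gives no figure of its own here, so there is none to reproduce. Inputs:

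- Rate: section 3.6 reports the "incidence of CLABSI per 1000 catheter days in the first 6 months of 2022, to be 12.18", that is 0.01218 per catheter-day.
- Patients: 50 per arm (section 3.6, before the drop-out allowance), with 55 as a check.
- Target: a 30% reduction (section 3.6), read as a rate ratio of 0.70.
- Catheter-days per patient, d: not stated. Assumed 7, 10 and 14.
- No true effect: both arms at 0.01218.

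Per arm, catheter-days T = 50 × d and expected CLABSIs E = 0.01218 × T. If k CLABSI patients, each with d catheter-days, are removed from the impregnated arm only, the apparent rate ratio is [(E − k)/(T − k·d)] / (E/T). Removal from control only gives the reciprocal.

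Example, d = 10 and k = 2: (6.09 − 2)/(500 − 20) = 4.09/480 = 0.00852, and 0.00852/0.01218 = 0.70.

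| | d = 7 | d = 10 | d = 14 |
|---|---|---|---|
| T, 50 per arm | 350 | 500 | 700 |
| E per arm | 4.26 | 6.09 | 8.53 |
| One removed, impregnated arm only | 0.78 | 0.85 | 0.90 |
| Two removed, impregnated arm only | 0.55 | 0.70 | 0.80 |
| Two removed, control arm only | 1.81 | 1.43 | 1.25 |
| Two from impregnated, one from control | 0.71 | 0.82 | 0.89 |
| Same number from each arm | 1.00 | 1.00 | 1.00 |
| Two removed, impregnated arm only, 55 per arm | 0.60 | 0.73 | 0.82 |

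**Significance.** Rounding the d = 10 case to 4 CLABSIs in 480 days against 6 in 500, the exact conditional test (4 of 10 events, null probability 480/980 = 0.49) gives p = 0.75.

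**The 48-hour rule.** Dropping five event-free patients with at most 2 days each from one arm raises its rate by at most T/(T − 10): 350/340 = 1.03, 500/490 = 1.02, 700/690 = 1.01.

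**A less extreme model.** Suppose a fraction f of patients are poorly compliant and carry r times the risk of the rest, with overall 10-day risk 1 − exp(−0.01218 × 10) = 0.1147 in both arms. Compliant patients then have risk q = 0.1147/(f·r + 1 − f). If a fraction x of the poorly compliant are dropped, the remaining risk is q[f(1 − x)r + 1 − f]/[f(1 − x) + 1 − f]. Dropping all of them in the impregnated arm and half in control gives:

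- f = 0.1, r = 2: 0.1042/0.1097 = 0.95
- f = 0.3, r = 3: 0.0717/0.0970 = 0.74

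Equal dropping gives 1.00. The values of f, r and x are assumptions.

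**The case against.** The strongest reply is that the documents never say such patients will leave the analysis. That is true: removal is an inference from their listing as exclusion criteria. It is the ordinary meaning of an exclusion, though, and nothing in the plan prevents it. The defect is a rule that permits bias, not proof that bias will occur.

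Second, removing only CLABSI patients from only one arm is a worst case. This stands as a limit on the size. Removals in both arms give smaller shifts, and equal removals give none. With 50 per arm, two one-sided removals reach 0.70 at 7 and 10 days but not at 14, where three are needed: (8.526 − 3)/(700 − 42) = 0.0084, and 0.0084/0.01218 = 0.69. One removal never reaches it. With 55 per arm, the number randomised, two removals reach it only at 7 days.

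Third, section 3.9 plans tests of proportions and a logistic model, whereas the illustration uses a rate ratio. It uses the scale on which section 3.7.1.1 defines the primary outcome; the effect on the planned tests was not calculated.

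Fourth, the dwell bullet is nearly harmless to the rate, and the bullet on additional lines can fairly be read as a screening criterion. Both points are accepted, and the case does not depend on either.

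Fifth, section 3.7.2 need not be exhaustive, and section 3.8.1 promises a form covering all study parameters, so compliance may be recorded. Possibly, but it is not named, and recording it would not supply a definition or an analysis rule.

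**Conclusion.** The concern holds and must be fixed before recruitment. It rests on the compliance criterion and the missing analysis population; the dwell rule is a minor instance and the additional-line bullet an ambiguity.

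The likely size is unknown, because the documents give neither catheter-days per patient nor a removal rate. Under the stated assumptions, two one-sided removals can shift the rate ratio by an amount comparable to the planned 30% reduction, in either direction. This concerns the validity of the estimate, not a false significant result. Exclusions already made unmasked could not be reliably undone at analysis.

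**What to change.** **Section 3.4.** Remove the compliance and under-48-hour bullets as grounds for excluding a randomised patient. Limit the additional-line bullet to a need known before randomisation.

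**Section 3.9.** State that the primary analysis includes all randomised patients in their assigned arm. Patients in whom no study catheter was inserted contribute no catheter-days and are reported by arm. Count CLABSIs and catheter-days by one pre-specified rule that also covers time with an additional or replacement line. For example, such time stays in the assigned arm in the primary analysis, and a sensitivity analysis censors at the first such line.

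**Data collection.** Define bundle compliance and have it recorded without knowledge of culture results. Report dwell time, compliance and additional lines by arm, and use them only in a pre-specified per-protocol sensitivity analysis.

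**Cost.** Protocol wording and a few form fields for compliance and additional lines; dwell is already needed for the primary rate. Outcome follow-up continues for patients who would otherwise have been dropped. The downside is some dilution of the effect by non-compliance and additional lines.

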3.5 Sampling Method

All adult patients who require a CVC insertion as part of their standard routine treatment in ICU will be recruited. After the recruitment, the patients will be randomly assigned to one of the two different groups using a computer: control group who receives non-impregnated CVC and investigational group who receives antimicrobial-impregnated CVC.

3.6 Sample Size

Our local data at ICU, UMMC reported the incidence of CLABSI per 1000 catheter days in the first 6 months of 2022, to be 12.18. Using SAS® for sample size calculation, in order to detect a clinically significant reduction of CLABSI by 30%, and assuming a two-sided type I error protection of 0.05 and a power of 0.80, we calculated a sample size of 50 patients is required. To incorporate a 10% drop out rate, we therefore aim to recruit 55 patients in each arm (antimicrobial-impregnated CVCs, n=55; non-impregnated CVCs, n=55). This will make up to a total sample size of 110.

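### Section 3.6 claims 80% power with 50 patients per arm, but its own inputs require about 12,200 catheter-days per arm, or about 243 per patient

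*Combined protocol and SAP*

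**What the plan says.** Section 3.6 (Sample Size) takes its control rate from local ICU data: "the incidence of CLABSI per 1000 catheter days in the first 6 months of 2022, to be 12.18". The target is set "in order to detect a clinically significant reduction of CLABSI by 30" per cent. The section continues: "assuming a two-sided type I error protection of 0.05 and a power of 0.80, we calculated a sample size of 50 patients is required". A 10% allowance for dropout raises this to 55 in each arm and 110 in total, so the 50 is per arm. SAS is named, but no procedure, test, mean catheter duration or expected number of CLABSIs is given.

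Other sections bear on the figure:

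- Section 3.7.1.1 makes the primary outcome a rate per 1000 catheter-days.
- Section 3.4 excludes "Patients who require > 1 CVC or other central venous access".
- Section 3.2 says: "The study will be conducted over a period of one year". The Gantt chart shows recruitment and data collection over the same 12 months.
- Section 3.9 says: "Categorical variables will be expressed as percentages and compared using the Chi-square or Fisher's exact test, whichever is appropriate". It adds logistic regression for risk factors and plans no comparison of rates.

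**The concern.** The information in a rate comparison comes from events, and so from catheter-days. A number of patients gives power only through the catheter-days that each contributes, and the plan never states that link. At 12.18 per 1000 catheter-days, 50 patients per arm yield only a handful of CLABSIs for any ordinary catheter duration, far too few to detect a 30% reduction.

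This is the only sample-size justification for the primary objective. If the reduction is real, the trial will most likely return a non-significant result. Anyone relying on the stated 80% power would then take that result as evidence against a 30% benefit, which it would not be.

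**Working it through.** **Inputs.** All are from section 3.6 unless noted.

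- Control rate λ₁ = 12.18/1000 = 0.01218 per catheter-day.
- Rate after a 30% relative reduction: λ₂ = 0.70 × 0.01218 = 0.008526. The difference is 0.003654 and the sum 0.020706.
- Two-sided alpha 0.05 and power 0.80: (1.96 + 0.8416)² = 7.849.
- 50 per arm, 55 with dropout.
- Mean dwell is not in the documents. It is assumed below at 7, 10, 14, 20 and 30 days.

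**Step 1: trying to reproduce 50.** None of the readings tried that use the 12.18 input gives 50 per arm.

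| Reading | Result |
|---|---|
| 12.18% vs 8.526% of patients, two proportions | about 1,090 per arm (1,145 with continuity correction) |
| 1.218% vs 0.8526%, two proportions | 12,045 per arm |
| Two rates, one-sided alpha | 9,588 catheter-days per arm; 192 per patient at 50 |
| Two rates, 50 taken as the total | 487 catheter-days per patient |
| Two rates, rate ratio 0.30 instead of 0.70 | 1,710 catheter-days per arm; 34 per patient at 50 |
| 30-point absolute change | A fall from 12.18% goes below zero; a rise to 42.18% gives 34 per arm (40 with correction) |

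Figures near 50 do appear with inputs the plan does not contain. Examples are 65% vs 35% with continuity correction (49), a 30% relative reduction from a risk of about 84%, and a comparison of means with an SD of about 6.5.

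**Step 2: exposure required.** For two Poisson rates,

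T per arm = (z₀.₉₇₅ + z₀.₈₀)² (λ₁ + λ₂)/(λ₁ − λ₂)² = 7.849 × 0.020706/0.003654² = 12,172 catheter-days.

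The log-rate form gives 12,302. Expected CLABSIs are 12,172 × 0.01218 = 148 and 12,172 × 0.008526 = 104. Per patient, 12,172/50 = 243 catheter-days, or 12,172/55 = 221. No dwell assumption enters this step.

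**Step 3: exposure available.** Patients needing more than one catheter are excluded, so these days must come from one catheter each. If recruitment is even over 365 days and data collection ends with it, mean observation is at most 365/2 = 183 days, even if no catheter were removed before the study ended. Without assuming even recruitment, a mean of 243 days needs an average entry day no later than 365 − 243 = 122, again with every catheter in place to the end.

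**Step 4: power at the planned size.** The range covers four tests: Fisher's exact and uncorrected chi-square on patient proportions 1 − exp(−λd), by full enumeration; the exact conditional test on Poisson counts; and the Wald test on the log rate ratio. Patients needed are T/d, before dropout.

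| Mean dwell d (assumed) | Expected CLABSIs at 50 per arm | Needed per arm | Power at 50 per arm | Power at 55 per arm |
|---|---|---|---|---|
| 7 days | 4.3 vs 3.0 | 1,739 | 2.2–7.6% | 2.6–7.9% |
| 10 days | 6.1 vs 4.3 | 1,218 | 3.5–8.7% | 4.1–9.1% |
| 14 days | 8.5 vs 6.0 | 870 | 5.2–10.5% | 5.8–10.8% |
| 20 days | 12.2 vs 8.5 | 609 | 7.5–12.6% | 7.8–13.3% |
| 30 days | 18.3 vs 12.8 | 406 | 10.5–16.5% | 11.3–17.7% |

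Worked example for Wald at 10 days and 50 per arm: SE = √(1/6.09 + 1/4.263) = 0.6315; |ln 0.70|/SE = 0.3567/0.6315 = 0.565; power = Φ(0.565 − 1.96) + Φ(−0.565 − 1.96) = 0.087.

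**Step 5: expected precision.** At 10 days and 50 per arm, the 95% interval around a rate ratio of 0.70 is 0.70 × exp(±1.96 × 0.6315), about 0.20 to 2.4. At 55 per arm it is about 0.22 to 2.3.

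**Step 6: the control rate that 50 per arm would need.** Setting λ₁ = 7.849 × 1.7/(0.09 × 50 × d) gives 0.297 per day at 10 days (297 per 1000, about 24 times 12.18) and 0.099 at 30 days (99 per 1000, about 8 times).

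**The case against.** The strongest reply is that section 3.6 names no procedure or follow-up time, so one cannot prove that no SAS calculation on these inputs returns 50. That is fair as far as it goes: only the readings tried can be excluded. But the error does not depend on finding where 50 came from. The stated inputs and endpoint fix the catheter-days required, and 50 patients cannot plausibly supply them.

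Second, the 183-day ceiling assumes even recruitment, which the plan does not state. Front-loaded recruitment would raise it. That stands, but a mean of 221 to 243 days would still need early entry and catheters kept in until the study closed.

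Third, every power percentage rests on an assumed dwell, and the ranges pool tests on two scales, whereas section 3.9 names only chi-square or Fisher's test for group comparisons. This also stands, which is why a range is shown. The highest figure anywhere in it is 17.7%, so neither choice rescues the claim.

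Fourth, the results for 55 per arm are best cases. They ignore the plan's own dropout allowance and the exclusions that can apply only after insertion (catheter in place under 48 hours, poor bundle compliance). The 50-per-arm figures are the ones to rely on.

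**Conclusion.** The concern holds and must be fixed. On the plan's own inputs, 80% power needs about 12,200 catheter-days per arm, or 243 per patient at 50 per arm and 221 at 55. This rests only on a Poisson comparison of two rates and on reading the 30% as a relative reduction.

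Actual power is about 2% to 17% at 50 per arm and 3% to 18% at 55, over assumed mean dwells of 7 to 30 days and four tests. Equivalently, at 50 per arm a true 30% reduction would be missed about 91% to 96% of the time at 10 days, and about 84% to 89% at 30 days. Nothing elsewhere in the document repairs the figure.

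**What to change.** In section 3.6:

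- Withdraw the 80% power claim.
- State the assumed mean dwell and its source. The local data behind the 12.18 figure must include catheter-days; if they also include catheter counts, the mean dwell follows.
- State the expected catheter-days and CLABSIs per arm.
- State the resulting power at the planned size for one named test. Until a dwell is justified, give the range: about 2–17% at 50 per arm, or 3–18% if all 55 are analysed, for 7 to 30 days.

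In section 3.9:

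- Add that the CLABSI rate ratio will be reported with its 95% confidence interval, and give the precision expected (at 10 days and 50 per arm, about 0.20 to 2.4 around 0.70).
- State that a non-significant result will not be read as no difference between catheters.

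Calling the trial a pilot or estimation study would be consistent with this but is optional.

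The cost is protocol wording and a far less favourable stated power. No extra patients are needed for this correction. It makes the claim accurate but leaves the primary comparison with the same low power.
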